Abbreviated Title: RCT of CDH1 Surveillance

Version Date: 03/12/2024

Abbreviated Title: RCT of CDH1 Surveillance

NIH Protocol #: 20C0150

Version Date: 03/12/2024

NCT Number #: NCT04535414

Title: Phase II Randomized Trial of Bethesda Protocol Compared to Cambridge Method for Detection of Early Stage Gastric Cancer in *CDH1* Mutation Carriers

NCI Principal Investigator: [name]
Surgical Oncology Program (SOP), CCR, NCI, NIH
[name]
[name]
[name]
[contact]
Email: [contact]

PRÉCIS

Background:

- Hereditary Diffuse Gastric Cancer (HDGC) is most often attributed to inactivating germline mutations in the E-cadherin (*CDH1*) tumor suppressor gene. Mutation carriers have a 24-70% lifetime risk of developing gastric adenocarcinoma.
- International consensus guidelines recommend endoscopic screening and surveillance of *CDH1* mutation carriers who decline risk-reducing total gastrectomy (TG). However, this approach lacks sufficient sensitivity for detection of occult, intramucosal foci of signet ring cancer cells (SRCC), which are pathognomonic of HDGC. Our team has established a systematic endoscopic screening protocol (Bethesda protocol) that demonstrates a higher rate of SRCC detection compared to historic controls using the currently recommended Cambridge method.

Objective:

- Determine if Bethesda protocol provides improved sensitivity for detection of early-stage gastric cancer in *CDH1* germline mutation carriers compared to the Cambridge method.

Eligibility:

- Subjects with pathogenic or likely pathogenic *CDH1* germline mutation.
- Age ≥ 18 years.
- Physiologically able to undergo upper endoscopy

Design:

- Phase II randomized study to compare Bethesda protocol and Cambridge method for detection of intramucosal SRCC in asymptomatic *CDH1* mutation carriers undergoing endoscopic screening or surveillance.

TABLE OF CONTENTS

TABLE OF CONTENTS	3
STATEMENT OF COMPLIANCE	10
1 INTRODUCTION	10
1.1 Study Objectives	10
1.1.1 Primary Objective	10
1.1.2 Secondary Objective	10
1.1.3 Exploratory Objectives	10
1.2 Background and Rationale	11
1.2.1 Study Disease	11
1.2.2 Annual Endoscopic Surveillance	13
1.2.3 Adjuncts to Endoscopy	14
1.2.4 Molecular and Physiologic Sequelae of Hereditary Diffuse Gastric Cancer Syndrome	15
2 ELIGIBILITY ASSESSMENT AND ENROLLMENT	16
2.1 Eligibility Criteria	16
2.1.1 Initial Enrollment	16
2.1.2 Re-Enrollment	16
2.1.3 Recruitment Strategies	16
2.2 Screening Evaluation	17

1 INTRODUCTION

1.1 STUDY OBJECTIVES

1.1.1 Primary Objective

- Determine if Bethesda protocol provides improved sensitivity for detection of early-stage gastric cancer in *CDH1* germline mutation carriers compared to the Cambridge method.

1.1.2 Secondary Objective

- Define the false negative rate of SRCC detection using Bethesda protocol and Cambridge methods in patients who proceed to risk-reducing total gastrectomy.
- To estimate and compare the difference in crude cancer detection rates between endoscopy using the Bethesda protocol and the Cambridge method.

1.1.3 Exploratory Objectives

- Determine if confocal endoscopic microscopy (CEM) will afford greater sensitivity for detection of SRC foci in *CDH1* germline mutation carriers compared to the Cambridge method
- To characterize gastric tract microbiota of *CDH1* germline mutation carriers.
- To assess esophageal motility after total gastrectomy (in patients who pursue total gastrectomy)
- Apply machine learning algorithms to aid early gastric cancer detection using input from confocal endoscopic microscopy (CEM) images and histopathology images/results, and utilize image-to-image translation to enhance early cancer detection with CEM

1.2 BACKGROUND AND RATIONALE

1.2.1 Study Disease

Heredity diffuse gastric cancer (HDGC) accounts for approximately 1-3% of gastric cancers globally and is the most common familial form of gastric cancer [1]. Forty percent of HDGC cases are linked to inactivating germline mutations in the E-cadherin (*CDH1*) tumor suppressor gene [2]. Estimates of disease penetrance have demonstrated *CDH1* mutation carriers have a substantially elevated lifetime risk of developing gastric cancer, approximating 37-70% in men and 24-56% in women [3, 4].

The *CDH1* gene encodes the tumor-suppressor protein E-cadherin, which is a glycoprotein localized on the surface of epithelial cells at the adherens junctions [5]. E-cadherin functions to regulate cell-cell adhesion and intercellular communication, which is critical for cellular migration, proliferation, apoptosis and cell differentiation [6-10]. When E-cadherin function is compromised there is loss of cell polarity and epithelial architecture, which interferes with the integrity of the adherens junctions. *CDH1*-null epithelial cells may become inappropriately placed in the cellular matrix of the lamina propria resulting in the formation of signet ring cancer cells (SRCC) (**Figure 1** and **Figure 2**) [11]. It is postulated that gastric *CDH1*-null SRCC can exist for extended periods of time allowing for the accumulation of additional molecular alterations that lead to tumorigenesis and/or metastasis [12]. It is speculated that a second hit to this gastric mucosa, via mutations in *Smad4*, *RHOA*, or *TP53*, ultimately enables tumor cell invasion and metastatic potential [11, 13-15].

Because of the increased lifetime risk of developing gastric cancer, the International Gastric Cancer Linkage Consortium (IGCLC) recommends risk-reducing total gastrectomy to remove all gastric epithelium [3]. At the time of total gastrectomy almost all asymptomatic patients with *CDH1* mutations are found to have SRCC within the stomach. Since 2017, our team has evaluated more than 59 total gastrectomy explants and found 86% harbor SRCC (T1a gastric cancers) on final pathology. However, there is a scientific lack of understanding of how and why these SRCC become invasive cancer.

[figure not shown]

Figure 1. Schematic representation of the formation of signet ring cancer cells (SRCC) from the gastric mucosa in *CDH1* mutation carriers. Left is a diagram of a gastric pit, which comprises normal gastric mucosa. After second allele loss of *CDH1*, SRCC form and accumulate in the lamina propria (middle image). Then, additional loss of cellular regulation mechanism results in tumorigenesis (far right).

[figure not shown]

Figure 2. Microscopic image of signet ring cancer cells (black arrow) within the lamina propria of the gastric mucosa

1.2.2 Annual Endoscopic Surveillance

For patients who decline risk-reducing gastrectomy, annual endoscopic surveillance utilizing the Cambridge method is currently recommended by the IGCLC for management patients with pathogenic *CDH1* variants [3]. This endoscopy technique is performed over 30 minutes, using a white light high definition endoscope; it consists of mucosal biopsies of any visible lesions, testing for *H. pylori*, and 30 random mucosal biopsies from the prepyloric area, gastric antrum, transitional zone, body, gastric fundus, and gastric cardia. However, this technique is not sensitive as it repeatedly has shown to miss early diffuse gastric cancer (DGC) [16-20]. The SRCC detection rate with the standard, Cambridge, method ranges from 15-60% with false negative rates of 37%-84.6% [21-24]. This form of surveillance is unreliable because intramucosal SRCC foci are not visible with standard endoscopy because they make up less than 2% of the gastric mucosa and often measure less than 1 mm in diameter [17].

Our team developed a novel systematic endoscopic screening protocol (Bethesda protocol) that was adapted from a method initially described by Yao [25]. Using white-light upper endoscopy, the Bethesda protocol consists of 88 mucosal biopsies taken from 22 anatomic areas of the stomach. Our group recently compared the sensitivity of SRCC detection using the Bethesda protocol to that of the Cambridge method in a retrospective analysis (**Figure 3**) [21].

[figure not shown]

Figure 3. Sensitivity of SRCC detection comparing the Bethesda protocol to that of the Cambridge method in a retrospective analysis.

The analysis consisted of 110 patients with the *CDH1* mutation who were evaluated at NIH Clinical Center. All 110 patients underwent screening gastroscopy; 29 using the Cambridge method and 81 using the Bethesda protocol. Signet ring cancer cells were detected in 4 patients (13.8%) using Cambridge method and 29 (35.8%) with the Bethesda protocol. Over half (17/29) of the Cambridge method patients underwent prophylactic total gastrectomy, of whom 11 had SRCC identified on final pathology. Of those 11, only 2 were positive for SRCC on esophagogastroduodenoscopy (EGD) yielding an 82% (9/11) false negative biopsy rate and an overall sensitivity of 18% (2/11). Comparatively, 24 patients screened with the Bethesda protocol (24/81) later underwent prophylactic total gastrectomy, of whom 22 were found to have SRCC on final pathology. Of those 22, 13 were positive for SRCC on EGD giving the Bethesda protocol a 41% (9/22) false negative biopsy rate and an overall sensitivity of 59% (13/22) for detecting SRCC. Based on these data, we conclude the Bethesda protocol is likely better than the Cambridge method at detecting SRCC in asymptomatic *CDH1* mutation carriers.

Our primary objective with this prospective random-assignment study is to compare the Bethesda protocol (investigational) to the Cambridge method (control) for detection of early stage gastric cancer (e.g. SRCC) in asymptomatic CDH1 mutation carriers.

To fully understand the limitations of endoscopic gastric cancer surveillance, the false-negative cancer detection rate should be defined also, which is a secondary aim of the proposed study. This can only be done through complete pathologic examination of total gastrectomy explants from patients who choose to proceed to prophylactic surgery endoscopic surveillance.

1.2.3 Adjuncts to Endoscopy

Enhanced endoscopic techniques to increase cancer detection rates through improved mucosal visualization have been attempted. Confocal endoscopic microscopy (CEM) is a technique that is used with a standard endoscope to obtain *in vivo* histology images of gastrointestinal mucosa. Based on data from a Phase II study by our group (18-C-0141), we determined the SRCC detection rate of CEM was slightly improved compared to Cambridge method. Our preliminary results, which included 34 patients accrued over eight months, demonstrated detection rate of CEM to be 28.6% with false negative rate of 71.4%, which appeared only slightly better than 14.3% and 85.7%, respectively, with Cambridge method. It is possible that CEM could improve white light endoscopy detection methods when added to the Cambridge method, as in our Phase II study. Further exploration of CEM added to gastric surveillance is necessary to answer this question. Moreover, interpretation of confocal images obtained during gastric surveillance posed a challenge in our Phase II study. Our group is exploring the possible application of artificial intelligence to endoscopic and histopathologic findings to improve the sensitivity and specificity of gastric cancer diagnosis. Because our use of CEM showed low sensitivity for occult cancer detection, we believe that application of machine learning (i.e., computer models) based on the input provided by CEM imaging will improve our ability to accurately and reliably detect cancer. By incorporating the corresponding histopathology images obtained after gastric biopsy, we will essentially teach the computer how to reliably detect occult gastric cancer through an iterative process.

Accurate detection of early gastric cancer from endoscopic biopsies or total gastrectomy explants requires expertise in gastrointestinal pathology. Briefly, our NCI pathology colleagues have analyzed over 80 gastrectomy specimens and over 1,000 gastric biopsy specimens over the past 3 years. They have a working system for how they approach all of these patients' specimens, such as the use of initial H&E for screening of gastric biopsies followed by selective use of PAS stain. Most often, they are identifying clusters of cells, generally from 100 micrometers up to 1 centimeter in diameter. It is rare for us to identify single cells, but we have identified small areas of carcinoma *in situ*. The examinations are performed in a systematic manner established by our expert gastrointestinal pathologists. It is most frequently our aim to adhere to international gastric cancer linkage consortium guidelines for pathologic examination based on availability of resources ([name], *personal communication*). A Level 1 examination is the minimum suggested to obtain sufficient data for appropriate patient care (**Figure 4**). A Level 3 examination would be considered optimal for clinical reporting and support preservation of tissue for future research.

Levels of pathological examination depending on availability of resources			
Level	Level 1 Minimum required	Level 2 [level 1 plus...]	Level 3 [Level 2 plus...]
Morphologic	
 Pin out and photograph Sample margins and lymph nodes Sample tissue from all gastric zones Map blocks to photo Examine all slides 	
 Embed all mucosa, process to paraffin blocks. Cut a subset of blocks, sampling all gastric zones Examine sampled slides. 	
 Cut all blocks. Examine all slides.
Repeat	
 Sample tissue from all zones Map blocks Examine all slides 	
 Cut a subset of blocks, sampling all zones Examine sampled slides. 	
Stop	When invasive carcinoma is found or up to arbitrary limit for example 50 blocks	When invasive carcinoma is found, or up to arbitrary limit for example 50 slides.	When all mucosa is examined.
Report	Multiple of foci of pT stage carcinoma in xx% of mucosa examined microscopically	Number of foci of pT stage carcinoma in xx% of mucosa examined microscopically	Number of foci of pT stage carcinoma, all mucosa examined microscopically
Blocks	~ 20-50*	~ 120-270	~ 120-270
Slides	~ 20-50*	~ 20-50*	~ 120-270

Figure 4. Levels of pathological examination depending on availability of resources.

1.2.4 Molecular and Physiologic Sequelae of Hereditary Diffuse Gastric Cancer Syndrome

And, although most patients tolerate life without a stomach, post-gastrectomy syndromes remain poorly understood. This includes everything from malabsorption, urolithiasis, early and late dumping syndrome, and post-gastrectomy dysphagia. For instance, post-gastrectomy dysphagia in the absence of a mechanical cause (i.e., stricture) is present in a subset of these patients for unknown reasons and very little data exist regarding esophageal motility changes following total gastrectomy.

Very few studies have evaluated esophageal motility after total gastrectomy. The limited data available demonstrate that the majority of post-gastrectomy patients (13/20) were symptomatic (with complaints of reflux, dysphagia, or odynophagia) while all demonstrated pathological patterns of contraction on esophageal manometry [26]. Because of this observation of symptomatic dysphagia in the absence of mechanical abnormality (i.e., esophageal stricture), we propose esophageal manometry studies to understand the functional effects of total gastrectomy on the esophagus as part of this endoscopic surveillance protocol.

The advent of highly sensitive analytical methods in recent years has enabled detailed delineation of the gut microbiome in health and disease. Therefore, analysis of the gastric and fecal microbiome may aid our understanding of microbiome diversity and possible dysbiosis. Gastric lavage and gastric biopsy can be used to define and characterize the gastric microbiota. Recent

studies demonstrate a correlation with gastric cancer and opportunistic pathogens within the stomach, however the gastric microbiome of *CDH1* mutation carriers and the microbiome contribution to disease penetrance in this population is unknown [27, 28]. We plan to use pyrosequencing techniques to survey microbial diversity in patients' gastric and fecal samples. Prior to stool sample collection dietary recordings and detailed medication history will be collected from study participants. The association between specific microbiome maps and the occurrence of bacterial translocation will then be analyzed.

2 ELIGIBILITY ASSESSMENT AND ENROLLMENT

2.1 ELIGIBILITY CRITERIA

2.1.1 Initial Enrollment

2.1.1.1 Inclusion Criteria

- An individual who harbors a pathogenic, or likely pathogenic, *CDH1* germline variant.
Note: individuals with *CDH1* variant classified as any of the following are not eligible:
 - variant of uncertain significance
 - benign
 - likely benign.
- Age \geq 18 years.
- Physiologically able to undergo upper endoscopy.
- Ability of subject to understand and the willingness to sign a written informed consent document.

2.1.1.2 Exclusion Criteria

- Any clinical contraindication (e.g., known bleeding disorder, thrombocytopenia) to endoscopic biopsy.
- Unstable angina or recent (within 3 months) myocardial infarction.
- Any clinical contraindication to general anesthesia.

2.1.2 Re-Enrollment

2.1.2.1 Inclusion Criteria

- Subject must have previously been enrolled on the study and must have undergone endoscopy. Note: Subject may re-enroll only once after initial endoscopy performed
- Subject must have clinical need for a repeat endoscopy
- Prior on-protocol endoscopy must have occurred at least 6 months (+/- 2 weeks) and no greater than 18 months (+/- 4 weeks)

2.1.3 Recruitment Strategies

This protocol may be abstracted into a plain language announcement posted on NIH websites and on NIH social media platforms. Participants may also be recruited through self-referrals, physician referrals, and referrals from the NIH Clinical Center (CC) Office of Patient Recruitment.

2.2 SCREENING EVALUATION

2.2.1 Screening Activities Performed Prior to Obtaining Informed Consent

Minimal risk activities that may be performed before the subject has signed a consent include the following:

- Email, written, in person or telephone communications with prospective subjects
- Review of existing medical records to include H&P, laboratory studies, etc.
- Review of existing MRI, x-ray, or CT images
- Review of existing photographs or videos
- Review of existing pathology specimens/reports from a specimen obtained for diagnostic purposes

2.2.2 Screening Activities Performed After a Consent for Screening Has Been Signed

The following activities will be performed only after the subject has signed the consent for this study for screening. Assessments performed at outside facilities or on another NIH protocol within the timeframes below may also be used to determine eligibility once a patient has signed the consent.

Within 30 days prior to enrollment:

- Complete medical history and physical examination, including vital signs.
- Review of genetic test results performed in any outside lab if not already completed (Section [2.2.1](#)).

2.3 PARTICIPANT REGISTRATION AND STATUS UPDATE PROCEDURES

Registration and status updates (e.g. when a participant is taken off protocol therapy and when a participant is taken off-study) will take place per CCR SOP ADCR-2: CCR Participant Registration & Status Updates found at: <https://ccrod.cancer.gov/confluence/pages/viewpage.action?pageId=73203825>.

2.3.1 Screen Failures

Screen failures are defined as participants who consent to participate in the clinical trial but are not subsequently assigned to the study intervention or entered in the study. A minimal set of screen failure information is required to ensure transparent reporting of screen failure participants, to meet the Consolidated Standards of Reporting Trials (CONSORT) publishing requirements and to respond to queries from regulatory authorities. Minimal information includes demography, screen failure details, eligibility criteria, and any serious adverse event (SAE).

Individuals who do not meet the criteria for participation in this trial (screen failure) because of non-conclusive genetic test results may be rescreened.

2.3.2 Intervention Assignment Procedures (For Registration Purposes Only)

2.3.2.1 Cohorts

Number	Name	Description
1	Cohort 1	Subjects with pathogenic, or likely pathogenic, CDH1 germline mutation

2.3.2.2 Arms

Number	Name	Description
1	Arm 1	Bethesda protocol (investigational)
2	Arm 2	Cambridge method (control)

2.3.2.3 Arm Assignment and Randomization

Subjects in Cohort 1 will be randomized by CRO to Arm 1 or Arm 2. No stratification is planned.

2.4 BASELINE EVALUATION

Within 30 days prior to study procedure (does not need to be repeated if performed during Screening within designated time period):

- Physical examination, including weight and vital signs.

3 STUDY IMPLEMENTATION

3.1 STUDY DESIGN

This is a Phase II randomized study designed to compare the efficacy of the Bethesda protocol compared to Cambridge method for detecting signet ring cells within gastric mucosa of asymptomatic patients with *CDH1* mutations.

Upon study enrollment, subjects will be randomized to undergo upper endoscopy by either the Bethesda protocol technique (Arm 1) or Cambridge method (Arm 2).

Confocal endomicroscopy (CEM) of the gastric mucosa (Section 3.1.3) will be performed on enrolled subjects of both study arms unless otherwise indicated* until sufficient data for statistically accurate and reliable application of machine learning (i.e., computer models – refer to Section 5.3.6 for details), currently believed to total the first 50 enrolled participants. *CEM will not be performed in the following circumstances: participant allergy to the contrast (refer to Section 3.1.3), equipment not available or not functioning properly, or due to operating room scheduling issues/availability.

Note: Biopsies will be obtained as indicated below.

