Based on the prior experience with surveillance endoscopy, out of 110 patients, only 17+24=41 (37%) patients underwent a gastrectomy. To provide adequate patients to have a high probability of yielding 60 per arm who have a gastrectomy resulting in 48 with SRCCs, the study will randomize 175 patients to Bethesda protocol and 175 to Cambridge (350 total patients) in order to have 79% probability of obtaining 60 or more patients undergoing each procedure including gastrectomy, if the true probability of undergoing a gastrectomy is 37%. In practice, patients will continue to be randomized up to the limit of 350 total randomized patients, or until 48 patients on each arm have undergone a total gastrectomy and found to have SRCCs. Re-enrolled subjects will be counted separately at each enrollment/randomization.

All randomized patients who receive an endoscopy will have the crude cancer detection rates compared between the two methods. Data from a prior NIH trial indicated that the crude cancer detection rate was 15% using the Cambridge method and 36% using the Bethesda method, based on 26 and 109 evaluable patients respectively. In the present trial, if all 175 patients are required in each arm, then there would be 90.6% power to detect a difference with a two-sided 0.05 significance level between 15% and 30% crude cancer detection rates on the Cambridge method and the Bethesda protocol respectively. If only 135 evaluable patients undergo endoscopy using each method, there would be 81.0% power to detect a difference with a two-sided 0.05 significance level between 15% and 30% crude cancer detection rates.

Since January 2017 through September 2019, we have enrolled over 240 *CDH1* mutation patients on protocol 17-C-0043, performed over 145 surveillance endoscopies (12 performed in September 2019), over 61 risk-reducing gastrostomies (5 performed in September 2019). It is anticipated that more than 100 patients per year will be able to enroll onto this trial. Thus, accrual of up to 350 total subjects is expected to be completed in no more than 3.5 years.

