8.3 POPULATIONS FOR ANALYSES

All patients who are randomized on the trial and receive an endoscopy will be used for analysis. Those who undergo gastrectomy will be included in the evaluation of the two methods relative to the biopsy proven results.

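### The arm is assigned at enrolment, with no limit on the wait for endoscopy and no rule to withhold it, and anyone not endoscoped leaves the analysis: randomising on the day would close this cheaply

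*Combined protocol and SAP*

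**What the plan says.** - **Timing of assignment.** Section 3.1: "Upon study enrollment, subjects will be randomized to undergo upper endoscopy". Section 2.3.2.3 adds only: "Subjects in Cohort 1 will be randomized by CRO to Arm 1 or Arm 2. No stratification is planned". Section 3.3.1 randomises again for a repeat endoscopy and gives no timing.
- **Knowledge of the arm.** No section masks the patient or the team, says when the patient learns the arm, or holds the assignment back until the procedure.
- **Time windows.** Section 2.2.2 dates the screening assessments: "Within 30 days prior to enrollment". Section 2.4 dates the baseline physical examination: "Within 30 days prior to study procedure (does not need to be repeated if performed during Screening within designated time period". Neither runs from randomisation to endoscopy.
- **Ways out.** Section 3.5.1 allows removal from the intervention at the patient's request or at the investigator's discretion.
- **Who is analysed.** Section 8.3: "All patients who are randomized on the trial and receive an endoscopy will be used for analysis". Section 8.2 repeats this for the secondary endpoint: "All randomized patients who receive an endoscopy will have the crude cancer detection rates compared between the two methods". No rule covers patients who are randomised but not endoscoped, and no all-randomised analysis is planned.
- **Cap.** Section 8.2 stops randomisation at 350 in total, or once 48 patients per arm have had a gastrectomy with SRCC found.

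**The concern.** Membership of the analysis set depends on an event after randomisation, namely reaching endoscopy, and knowledge of the arm can influence that event. The team is not neutral between the methods: Section 1.2.2 describes the Cambridge method as insensitive and concludes that the Bethesda protocol is probably better. A patient or investigator who knows the arm therefore has a reason to act on it before the procedure.

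Two things are at stake. First, if the loss differs between arms and is related to whether biopsy would find SRCC, the crude detection rates no longer compare randomised groups. Second, a patient lost before endoscopy uses one of the 350 places and contributes nothing to either endpoint, whether or not the loss is selective.

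**Working it through.** **1. Inputs from Section 8.2.** 175 randomised per arm; gastrectomy probability 37%; target of 60 gastrectomies per arm; crude detection 15% against 30%; two-sided 0.05. Section 8.4.3 specifies Fisher's exact test.

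**2. The plan's own figures reproduce.** Power was computed by summing the two binomial distributions over all tables that Fisher's test rejects; the yield is a binomial tail.

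| Quantity | Stated | Recomputed |
|---|---|---|
| Power, 15% v 30%, 175 per arm | 90.6% | 90.65% |
| Power, 15% v 30%, 135 per arm | 81.0% | 80.99% |
| Power, 30% v 60%, 48 per arm | 80% | 80.05% |
| P(at least 60 gastrectomies), 175 patients, 37% | 79% | 79.4% |

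None of these figures is in dispute.

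**3. Non-selective loss, same rate in both arms (rates assumed).** The 37% is 41/110, and Section 1.2.2 says that all 110 patients had a gastroscopy. It is thus a rate among endoscoped patients, and applying it to all 175 assumes that nobody is lost first. With loss d, n = 175 × (1 − d), and the yield is P(X ≥ 60) for X ~ Binomial(n, 0.37).

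| Loss d | n per arm | P(at least 60), per arm | Power, 15% v 30% |
|---|---|---|---|
| 0 | 175 | 79% | 90.6% |
| 5% | 166 | 62% | 89.1% |
| 10% | 158 | 43% | 87.3% |
| 20% | 140 | 9% | 82.8% |

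Power for crude detection changes little. The gastrectomy yield is the sensitive quantity.

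**4. Selective loss in the control arm only (all inputs assumed).** Let the true detection rate p be equal in both arms, and let leavers be r times as likely to be positive. The observed control rate is p × (1 − d × r)/(1 − d). Example: p = 0.25, d = 0.10, r = 2 gives 0.25 × 0.80/0.90 = 22.2%, a false difference of 2.8 points. Fisher's test is then applied to 175 Bethesda patients and 175 × (1 − d) control patients.

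| True rate p | Loss d | r | Observed control | False difference (points) | Type I error |
|---|---|---|---|---|---|
| 15% | 0 | – | 15.0% | 0 | 3.6% |
| 15% | 5% | 2 | 14.2% | 0.8 | 4.5% |
| 15% | 10% | 2 | 13.3% | 1.7 | 6.1% |
| 25% | 0 | – | 25.0% | 0 | 3.8% |
| 25% | 5% | 2 | 23.7% | 1.3 | 5.1% |
| 25% | 10% | 1.5 | 23.6% | 1.4 | 5.2% |
| 25% | 10% | 2 | 22.2% | 2.8 | 8.1% |

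With r = 1 (loss unrelated to SRCC), the false difference is zero and the type I error stays between 4.1% and 4.4%. The same loss in the Bethesda arm would pull the comparison the other way.

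**5. Effect of the fix on the design.** Assigning the arm on the day changes no sample size. Patients lost earlier are then never randomised and take no place under the cap.

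**The case against.** The strongest reply is that the mechanism is possible but undocumented. Most of that stands.

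- **The interval.** A reader might infer a gap of up to about 30 days from "Within 30 days prior to study procedure". The documents do not support this: that window limits the age of the physical examination, and the one in Section 2.2.2 precedes enrolment. The gap is unspecified and may be short or long.
- **Knowledge of the arm.** That patients learn the arm in advance is inferred from silence. Only the endoscopist must know it.
- **Expected drop-out.** A reader might take "If only 135 evaluable patients undergo endoscopy using each method" as an admission of 23% loss (40/175). It applies to both methods and follows the rule that lets randomisation end early, so it most naturally describes accrual stopping before 350.
- **Direction.** A reader might assume that control patients leave and Bethesda gains. But Arm 1 takes 88 biopsies over about 45 minutes, against at least 30 over about 30 minutes, and Cambridge is the guideline method, so loss could go either way.
- **Reach.** A reader might extend the bias to every analysis. The primary endpoint is sensitivity among patients with SRCC in the explant, and no direction or size can be derived for it from pre-endoscopy loss. Choosing gastrectomy after a known biopsy result is a separate and probably larger selection.
- **Choice of population.** A patient without an endoscopy has no detection result, so restricting the analysis to endoscoped patients is ordinary. Off-study status is also registered under Section 2.3. What is missing is reporting by arm.

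The reply does not remove the gap itself: assignment comes first, nothing limits or conceals it, and those lost in between drop out of the analysis without being reported by arm.

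**Conclusion.** The point holds as a cheap improvement, not as a demonstrated bias. Arm-dependent loss before endoscopy is possible under the stated rules and would be excluded from the analysis. It biases crude detection only if it is both unequal between arms and related to SRCC status. Under the assumed 5% to 10% control-only loss, with leavers twice as likely to be positive, the type I error is about 4.5% to 8%, against 3.6% to 3.8% without loss. Much larger inflation needs loss that is at once large, one-sided and strongly selective, and nothing in the documents suggests that.

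The yield cost needs no selectivity: 79% falls to about 62%, 43% or 9% per arm at 5%, 10% or 20% loss. It rests on the plan's 37% holding among those endoscoped and on the 350 cap being reached. All loss rates are assumptions. No bias is quantified for the primary endpoint.

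**What to change.** 1. In Section 3.1, replace "Upon study enrollment, subjects will be randomized to undergo upper endoscopy" with a statement that CRO randomises on the day of endoscopy, once baseline assessments are complete.
2. Add the same timing to Section 2.3.2.3 and to Section 3.3.1, so that it covers first and repeat endoscopies.
3. Book every slot at the longer arm's length (about 45 minutes), plus confocal imaging time where that is planned, so that scheduling does not depend on the arm.
4. In Section 8.3, state that patients are analysed by assigned arm, and that those randomised but not endoscoped are reported by arm with reasons.

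If same-day release is not workable, set a maximum interval from randomisation to endoscopy, keep item 4, and add an all-randomised sensitivity analysis for crude detection. Such an analysis cannot recover primary sensitivity, which needs an explant.

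Cost: a short amendment, a same-day release by CRO, and about 15 minutes of unused slot time per control patient (45 − 30). The sample size and the stated power do not change.
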